The Phase III clinical program of the dapivirine vaginal ring, containing 25 mg of dapivirine (Ring-004), consists of the MTN-020 and IPM 027 clinical trials. These trials are conducted in South Africa, Uganda, Zimbabwe and Malawi, to assess the safety and efficacy of the Dapivirine Vaginal Ring-004 in preventing the acquisition of HIV-1 infection through male to female transmission in healthy, HIV-negative women.

IPM 027 is a double-blind, multicentre, placebo-controlled trial that has been designed to assess the safety and efficacy of the Dapivirine Vaginal Ring-004, inserted once every 4 weeks over a period of 24 months, in healthy, sexually active HIV-negative women, 18 to 45 years of age, when compared to a placebo vaginal ring. It is conducted at 7 research centres, six in South Africa and one in Uganda. A total of 1959 eligible women were randomized in a 2:1 ratio to receive either the dapivirine vaginal ring or placebo vaginal ring. This trial was initiated in March 2012 and is expected to complete in 2016/2017.

MTN-020 has been designed to assess the safety and effectiveness of the Dapivirine Vaginal Ring-004, inserted once every 4 weeks, in healthy, sexually active, HIV-negative women, 18 to 45 years of age, when compared to a placebo vaginal ring. It is conducted in Malawi, South Africa, Uganda and Zimbabwe. A total of 2629 women were

randomized. Each participant will use the investigational product until 120 events (HIV-1 seroconversions) are observed in the trial. All participants are anticipated to use the investigational product for a minimum of 12 months. The trial was initiated in August 2012 and clinical conduct completed in June 2015.

1.4.3. *Adherence to and Acceptability of the Dapivirine Vaginal Ring*

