Residual levels of dapivirine in returned rings and/or plasma and/or vaginal fluid concentrations of dapivirine will be used as measures of adherence to ring use. The data will be listed, summarised and presented graphically. Participants will be categorized as either adherent or non-adherent, based on these measures. The ring residual levels and/or plasma and/or vaginal fluid concentrations of dapivirine associated with non-adherence will be informed by the results from IPM 027, and will be described in detail in the SAP, which will be finalised prior to final database lock. The correlation between the amount of residual dapivirine in the used rings and the corresponding plasma and/or vaginal fluid levels of dapivirine will be explored graphically and summarised descriptively.

8.4.3. *Secondary Analyses*

8.4.3.1. *Incidence of HIV-1 seroconversion*

The incidence of HIV-1 seroconversions, the incidence density rate of HIV-1 seroconversion, i.e. HIV-1 seroconversion rate per 100 woman-years of product use at the end of the ring use period, as well as a 95% CI for the HIV-1 seroconversion rate per 100 woman-years based on the normal approximation of the Poisson distribution will be presented for each research centre, and overall. Kaplan-Meier curves will be presented, stratified by research centre.

8.4.3.2. *HIV-1 drug resistance*

The analysis of HIV-1 drug resistance will be primarily descriptive in nature, and will depend on the pattern of resistance mutations observed in the HIV-1 seroconverters. The resistance associated mutations observed will be listed by participant, and a frequency tabulation of individual resistance mutations associated with the various

classes of antiretrovirals, e.g. Protease Inhibitors, Nucleoside Reverse Transcriptase Inhibitors and Non-nucleoside Reverse Transcriptase Inhibitors, will be produced. The proportion of HIV-1 seroconverters with at least one HIV-1 drug resistant mutation will be presented, with the corresponding 95% CI.

8.4.4. *Interim Analysis*

No interim analysis is planned for this trial. However, the Sponsor will review the treatment emergent safety data at regular intervals during the conduct of the trial.

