3 TRIAL DESIGN

3.1 General Design and Plan

IPM 032 is a Phase IIIb, multi-centre follow-on open-label trial to evaluate the continued adherence to and safety of the Dapivirine Vaginal Ring-004 inserted at monthly intervals in healthy, HIV-negative women who have participated in the IPM 027 Phase III Dapivirine Vaginal Ring-004 trial. All women who have participated in IPM 027 and are HIV-negative at screening for IPM 032, will be eligible. It was estimated that approximately 1400 participants will be enrolled.

All participants will attend a research centre follow-up visit one month after enrollment. Following this visit, at the investigator's discretion, a participant can continue on a 3-monthly visit schedule. Monthly visits may however be extended up to the first three months of participation. Once the 3-monthly trial visit schedule commences, three rings will be dispensed to the participant. One ring will be self-inserted at the research centre and two additional rings will be dispensed for the participant to take home, or dispensing will take place as arranged with the participant.

Each participant will engage in the screening process for up to 45 days prior to enrollment and will use the Dapivirine Vaginal Ring-004 for a period of up to 12 months. IPM will have the option to extend this trial period. Accrual was expected to take place over approximately 6 months; participants enrolled more than 6 months after the onset of the study site's accrual period may have a shortened follow-up period.

Each participant will have an exit visit 1 to 2 months after ring discontinuation, to assess safety and identify HIV-1 seroconversions after product discontinuation.

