9 EVALUATION OF TRIAL ENDPOINTS

9.1 Primary Endpoint 1 – Safety

The analysis of AEs will be mainly descriptive in nature. That is, the number and percentage of participants experiencing AEs will be presented per SOC and PT, overall and by research centre. The proportion of participants experiencing the following will be determined and summarized:

- AEs considered by the Investigator as related to IP
- Grade 3 or 4 AEs
- SAEs

For these three endpoints, and for the most frequently reported AEs (*i.e.* AEs occurring in at least 5% of participants overall) the proportion and the corresponding 95% confidence interval will be presented for the overall counts. The confidence interval will be determined using Fisher's exact test.

Separate tabulations will be created for AEs of special interest (selected urogenital AEs and STIs). For this purpose, PTs may be grouped into categories of interest (refer to Appendix 5).

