- Analysis 3: All confirmed HIV-1 seroconverters determined to have been HIV-1 infected after enrollment will be considered as infected on product, even in instances where HIV-1 seroconversion and estimated point of infection was determined to be after the last product use visit.
- Analysis 4 (HIV-1 infection rate): Similar to Analysis 1, but based on time to first positive HIV-1 RNA.

All additional analyses will be performed on the m-ITT population.

For the number of participants included in the m-ITT analysis in IPM 032, matching placebo participants will be resampled with replacement from the IPM 027 trial, based on research center, age and STI prevalence at screening. These factors were selected because of their strong association with HIV incidence.

Age categories (18-24, and \geq 25 years) will be used to ensure that a sufficient number of participants are represented in each combination of categories of age, center and STI prevalence at screening (Yes/No). This resampling will be repeated 10 000 times; by ordering the 10 000 incidence rates and taking the 250th and 9750th value, a 95% confidence interval can be established. The placebo ring data of the complete double-blind period of IPM 027 will be used for this simulation.

The incidence of HIV-1 seroconversions, the incidence density rate of HIV-1 seroconversion (*i.e.* HIV-1 seroconversion rate per 100 person-years of product use at the end of the ring use period) as well as a 95% confidence interval for the HIV-1 seroconversion rate per 100 person-years (based on the normal approximation of the Poisson distribution) may be presented for the simulated placebo and treatment arm, overall and for each research centre. Similarly, the incidence of HIV-1 seroconversions, the incidence density rate and 95% CI will be presented by visit schedule (A, B or C) and overall. The 95% CI will be calculated using the formula below:

$$95\% \text{ confidence interval} = [(n/PY) \pm 1.96 \times (\sqrt{n/PY} / PY)] \times 100$$

where:

n = number of HIV-1 seroconversions

PY = total number of person-years of product use

Kaplan-Meier curves, of time to HIV-1 seroconversion will be presented, overall and by research centre using PROC LIFETEST in SAS®.

The time to event will be calculated as follows:

Time to event (days) = (Date of seroconversion/Censoring Date – Date of first ring use) + 1

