9.3.2 Secondary Endpoint 2: HIV-1 drug resistance mutations among participants who acquire HIV-1

Consistent with the secondary objective to evaluate HIV-1 drug resistance mutations among participants who acquire HIV-1 in the trial, secondary endpoint 2 is the proportion of HIV-1 seroconverters with drug resistant mutations.

Assessments

HIV viral genotyping will be performed on all HIV-1 seroconverters.

Statistical methods

The analysis of HIV-1 drug resistance will be primarily descriptive in nature, and will depend on the pattern of resistance-associated mutations (RAMs) observed in the HIV-1 seroconverters. The Stanford NNRTI Resistance Mutation Scores of Drug Resistance Mutations in HIV-1 (database version 8.4 - dated 2017-06-16) is provided in Appendix 4.

The number of RAMs observed will be listed by participant, and a frequency tabulation of individual RAMs associated with the various classes of antiretrovirals (Protease Inhibitors [PIs], Nucleoside Reverse Transcriptase Inhibitors [NRTIs] and Non-nucleoside Reverse Transcriptase Inhibitors [NNRTIs]) will be produced. The proportion of HIV-1 seroconverters with at least one HIV-1 drug resistant mutation will be presented overall, and by research centre, if possible, with corresponding 95% confidence intervals (using the Fisher's exact test).

If the data allows, the following frequency tabulations will be created:

- The number (and percentage) of participants who had a resistance test performed (pre-seroconversion, at seroconversion and at the Exit visit.)

- Reasons why a resistance test was not performed (if available in the database.)
- The number (and percentage) of participants with each individual mutation by class (NNRTI, NRTI, major PI.)
- The number (and percentage) of participants with 0, 1, 2, and ≥ 3 mutations by class (NNRTI, NRTI, major PI.)
- The number (and percentage) of participants with different mutational patterns (including single mutations), by class (NNRTI, NRTI, major PI.)
- Additional mutations (e.g. those selected by dapivirine in vitro but not included in the Stanford HIV database set) will be described.

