Table 14.3.7.5

Analysis 1, HIV-1 Seroconversion Rate per 100 Person-Years of Product Use

Population: m-ITT

	Statistic	IPM 027 Dapivirine (N=XXX)	IPM 027 Placebo (N=XXX)	IPM 032 Overall (N=XXX)
Number of confirmed HIV-1 seroconversions on IP	n (%) ^a	X (X.X)	X (X.X)	X (X.X)
Total number of person-years	PY	XXX	XXX	XXX
Seroconversion rate (per 100 person-years)	n/PY	XX.X	XX.X	XX.X
95% CI for seroconversion-rate (per 100 person-years)	95% CI ^b	XX.X, XX.X	XX.X, XX.X	XX.X, XX.X

Programmers Note: Please repeat the table for the PP population

CI = Confidence interval; HIV-1 = Human immunodeficiency virus type 1; IP = Investigational product

^a Percentages are calculated out of the number of participants in the applicable population per IPM 027 treatment

^b 95% CI calculated as $[(n/PY) \pm 1.96 \times ([n/PY] / PY)^{1/2}] \times 100$; where n = number of HIV seroconversions and PY = total number of person-years of product use calculated as PY = (Date of last ring removal – Date of first ring insertion + 1)/365.25

Table 14.3.7.6
 Analysis 2, HIV-1 Seroconversion Rate per 100 Person-Years of Product Use
 m-ITT

	Statistic	IPM 027 Dapivirine (N=XXX)	IPM 027 Placebo (N=XXX)	IPM 032 Overall (N=XXX)
Number of confirmed HIV-1 seroconversions on IP	n (%) ^a	X (X.X)	X (X.X)	X (X.X)
Total number of person-years	PY	XXX	XXX	XXX
Seroconversion rate (per 100 person-years)	n/PY	XX.X	XX.X	XX.X
95% CI for seroconversion-rate (per 100 person-years)	95% CI ^b	XX.X, XX.X	XX.X, XX.X	XX.X, XX.X

CI = Confidence interval; HIV-1 = Human immunodeficiency virus type 1; IP = Investigational product

^a Percentages are calculated out of the number of participants in the m-ITT population per IPM 027 treatment

^b 95% CI calculated as $[(n/PY) \pm 1.96 \times ([n/PY] / PY)^{1/2}] \times 100$; where n = number of HIV seroconversions and PY = total number of person-years of product use calculated as PY = (Date of last ring removal – Date of first ring insertion + 1)/365.25

In instances where it cannot be ruled out that HIV-1 infection may have occurred during IP use in case the HIV RNA test has detectable levels at the next visit after ring use, such participants will be considered as being seroconverted

Table 14.3.7.7
 Analysis 3, HIV-1 Seroconversion Rate per 100 Person-Years of Product Use
 m-ITT

Statistic	IPM 027 Dapivirine (N=XXX)	IPM 027 Placebo (N=XXX)	IPM 032 Overall (N=XXX)
Number of confirmed HIV-1 seroconversions on IP	n (%) ^a	X (X.X)	X (X.X)

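### The normal-approximation 95% CI for the HIV-1 seroconversion rate has no low-count rule: it collapses to 0 to 0 with no events and has a negative lower limit with 1 to 3 events

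*SAP*

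**What the plan says.** Protocol Section 8.4.3.1 names the interval for the rate per 100 woman-years as "based on the normal approximation of the Poisson distribution will be presented for each research centre, and overall". SAP Section 9.3.1 keeps the method but makes the centre breakdown optional: "based on the normal approximation of the Poisson distribution) may be presented for the simulated placebo and treatment arm", overall and by centre. The breakdown by visit schedule is not optional: "95% CI will be presented by visit schedule (A, B or C) and overall. The 95% CI will be calculated using the formula below".

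The footnotes of Tables 14.3.7.5 to 14.3.7.8 in SAP Appendix 1 give the interval as 100 × [(n/PY) ± 1.96 × ((n/PY)/PY)^(1/2)]. Those tables have a column for each former IPM 027 arm and one for IPM 032 overall. For Table 14.3.7.5 there is also the instruction "Please repeat the table for the PP population". The list of tables contains no rate table by schedule or by centre.

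For proportions the SAP uses exact limits. Section 9.1 says of the adverse event proportions: "The confidence interval will be determined using Fisher's exact test". Section 9.3.2 gives the resistance proportion among seroconverters "with corresponding 95% confidence intervals (using the Fisher's exact test").

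**The concern.** The normal approximation needs a reasonable number of events. The plan applies it to every cell, with no minimum count, no zero-event rule, no truncation and no alternative method. The nearest wording, in SAP Section 6.6, allows 95% intervals where appropriate, which does not say what happens at low counts.

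Some cells could be small. The schedule split is not fixed by design: after the first month, "at the investigator's discretion, a participant can continue on a 3-monthly visit schedule". The former-placebo column draws on the smaller arm of IPM 027: "A total of 1959 eligible women were randomized in a 2:1 ratio" in favour of dapivirine.

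This is the only interval planned for the IPM 032 rate itself; the 10 000-fold resampling gives an interval for the matched placebo rate. A schedule with no infections would be printed as if its rate were known exactly. One with 1 to 3 infections would carry an impossible lower limit and an upper limit that is too low, and the upper limit is the one that matters for infection on product.

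**Working it through.** The plan prints no interval, expected count or planned PY for this endpoint, so there is no figure of its own to reproduce.

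**Inputs.** From the documents: multiplier 1.96; n and PY as observed; about 1400 women; ring use up to 12 months; six centres in the table shells. Assumed: 1400 women × 1 year = 1400 PY, and true rates of 1, 2 and 4 per 100 PY.

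**Limits.** The footnote form simplifies to (n ± 1.96 × sqrt(n))/PY. The lower limit is negative when 0 < n < 1.96² = 3.84, so for n = 1, 2 and 3 at any PY. Exact limits in events are chi2(0.025; 2n)/2, set to 0 at n = 0, and chi2(0.975; 2n+2)/2.

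| n | Normal, in events | Exact, in events |
|---|---|---|
| 0 | 0 to 0 | 0 to 3.69 |
| 1 | -0.96 to 2.96 | 0.03 to 5.57 |
| 2 | -0.77 to 4.77 | 0.24 to 7.22 |
| 3 | -0.39 to 6.39 | 0.62 to 8.77 |
| 4 | 0.08 to 7.92 | 1.09 to 10.24 |

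Multiply by 100/PY for a rate. In one third of 1400 PY (467 PY), n = 3 gives -0.08 to 1.37 per 100 PY against an exact 0.13 to 1.88, and n = 0 gives 0 to 0 against 0 to 0.79. In 140 PY, n = 0 gives 0 to 0 against 0 to 2.63.

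**Coverage.** Add the Poisson probabilities of the counts whose interval contains the true mean.

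- Mean 1: counts 1 to 5 qualify, 63%.
- Mean 2: counts 1 to 7, 86%.
- Mean 3: counts 2 to 8, 80%.
- Mean 5: counts 3 to 11, 87%.

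Exact limits cover 98.1%, 98.3%, 98.8% and 98.0% at the same means. The normal interval recovers to 92.6% at mean 10 and 94.8% at mean 20.

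**How often counts are low.** P(n ≤ 3) from a Poisson with mean 1400 × share × rate/100. For a one-third share at rate 1 the mean is 4.67, and e^(-4.67) × (1 + 4.67 + 10.89 + 16.94) = 0.31.

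| Cell (assumed share of 1400 PY) | 1 per 100 PY | 2 per 100 PY | 4 per 100 PY |
|---|---|---|---|
| Schedule, one third | 31% | 2% | about 0% |
| Schedule, 10% | 95% | 69% | 19% |
| One of six equal centres | 79% | 31% | 2% |
| Former placebo arm, one third | 31% | 2% | about 0% |

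The last row assumes that both IPM 027 arms roll over equally. With 700 PY in total, each figure is the one for half the rate; the one-third schedule at 1 per 100 PY becomes 79%.

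**Overall rate.** At 20 events in 1400 PY the normal interval is 0.80 to 2.05 and the exact one 0.87 to 2.21 per 100 PY; the upper limits differ by 7%.

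**The case against.** The strongest reply is that nothing is miscalculated. The protocol and SAP name the same standard method, the endpoint is secondary and descriptive, and no test uses the interval. That stands and caps the severity. It does not answer the zero-event case or the coverage at low counts.

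Second, the small cells are supposed. The documents give no incidence, no PY total and no schedule split; investigator discretion permits an uneven split but does not show one. With equal schedules the problem is largely confined to rates near 1 per 100 PY or short follow-up. This also stands. A reader might infer that low counts are to be expected in this trial, and the documents do not support that.

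Third, exact limits over-cover, so part of the gap in the upper limits is the comparator's own conservatism. True, but the coverage of 63% to 87% is measured against 95%, not against the exact interval.

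Fourth, the formula displayed in SAP Section 9.3.1, as read from the file, has the root over n/PY only. Taken literally it still gives 0 to 0 at n = 0, but no negative limit at realistic PY. A reader might infer that the SAP holds a second, wrong formula. It conflicts with the method named in the same section and with four table footnotes, and is probably a conversion artefact, so it is not counted as an error. The negative-limit statement rests on the named method and the footnotes.

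**Conclusion.** The point holds and is minor. For the named method and the footnote formula, the 0 to 0 interval at no events and the negative lower limit at 1 to 3 events are certain; they depend on no assumption about PY. How often they would appear does depend on assumption: about 31% for a one-third schedule at 1 per 100 PY with 1400 PY in total, 2% at 2 per 100 PY, and more in smaller cells.

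The required schedule breakdown is exposed, as are the columns by former IPM 027 arm and any centre breakdown. Because no rate table by schedule or centre is listed, it cannot be assumed that readers will see n and PY there and recompute. A reader might go further and conclude that the overall incidence estimate, or its comparison with the resampled placebo rate, is unsound. The documents do not support that: the placebo rate has its own percentile interval, and at about 20 events or more the overall interval changes little.

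**What to change.** In SAP Section 9.3.1 and the footnotes of Tables 14.3.7.5 to 14.3.7.8, use exact Poisson limits for every IPM 032 rate (overall, schedule, centre, former IPM 027 arm, per-protocol) at any count:

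- lower = 100 × chi2(0.025; 2n)/(2 PY), set to 0 when n = 0
- upper = 100 × chi2(0.975; 2n+2)/(2 PY)

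One rule at all counts avoids choosing the method from the data and printing two different intervals for the same overall rate. Print n and PY beside each schedule and centre rate. Record the departure from the protocol's named method in SAP Section 11, which now reports no changes. When editing, make the formula shown in Section 9.3.1 agree with the footnotes.

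The cost is SAP wording, revised footnotes and a line of code. Exact limits are somewhat conservative and wider: at n = 3 in 1400/6 = 233.3 PY the width is 3.49 per 100 PY (0.27 to 3.76) against 2.91 (-0.17 to 2.74).

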3.2 Sample Size

This is an open-label, follow-on trial to IPM 027 to evaluate the safety of and adherence to the Dapivirine Vaginal Ring-004, inserted at monthly intervals in healthy, HIV-negative women who have participated in the IPM 027 trial. No formal sample size or power calculations have thus been performed. It was expected that approximately 70% of the participants enrolled in IPM 027 will participate in this trial. Therefore, a total sample size of approximately 1400 HIV-negative women was anticipated.

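### As printed, the 95% CI formula for the HIV-1 seroconversion rate in SAP section 9.3.1 is too narrow by a factor of √PY and disagrees with the correct formula in the table shells

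*SAP*

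**What the plan says.** SAP section 9.3.1 (Secondary Endpoint 1, statistical methods) describes the 95% interval for the seroconversion rate as "based on the normal approximation of the Poisson distribution". It then gives the formula "n/PY) \pm 1.96 \times (\sqrt{n/PY} / PY", with the whole multiplied by 100, defining "n = number of HIV-1 seroconversions" and "PY = total number of person-years of product use". The protocol (section 8.4.3.1) names the same method without a formula.

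The table shells in SAP Appendix 1 give the interval again. Footnote b of Tables 14.3.7.5 to 14.3.7.8, which cover Analyses 1 to 4, reads "n/PY) \pm 1.96 \times ([n/PY] / PY)^{1/2}] \times 100", with both divisions inside the bracket that is raised to the power one half.

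Section 9.3.1 plans this interval by visit schedule (A, B or C) and overall. It allows it, as an option, for the simulated placebo and treatment arms, overall and by centre. The four shells have columns only for the two IPM 027 treatment arms and IPM 032 overall, and the table list contains no other seroconversion-rate table.

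**The concern.** Two formulas for one interval differ in what lies under the root, so they cannot both be right. The one in section 9.3.1 does not follow from the method named in the sentence that introduces it. This is not the familiar weakness of Wald intervals at low counts, because the discrepancy is present at every n.

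At stake is the precision shown for secondary endpoint 1. A programmer working from section 9.3.1 would produce intervals so narrow that a handful of infections seem to fix the rate to the second decimal. For the rates without a shell, section 9.3.1 is the only place where the formula is stated.

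**Working it through.** **Inputs.** The two formulas come from the SAP as quoted. The documents give no event count, total person-years or numeric interval, so there is no figure of the plan's own to reproduce. For scale, SAP section 3.2 says "a total sample size of approximately 1400 HIV-negative women was anticipated", and section 3.1 allows up to 12 months of ring use. That is at most about 1400 × 1 = 1400 person-years before any extension. The shell footnotes name six centres, and 1400/6 ≈ 233, so 200 person-years is roughly centre size. The person-years (200 to 1400) and the rate (2 per 100 person-years) used below are assumptions.

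**Step 1: the standard error of the named method.** For a Poisson count, Var(n) is estimated by n. Hence SE(n/PY) = √n/PY.

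**Step 2: what each formula gives.**
- Footnote b: ([n/PY]/PY)^(1/2) = (n/PY²)^(1/2) = √n/PY. This agrees with step 1.
- Section 9.3.1: √(n/PY)/PY = √n/PY^1.5. This does not.
- Ratio, footnote b to section 9.3.1: (√n/PY)/(√n/PY^1.5) = √PY, whatever n is.

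**Step 3: one case in full, n = 28 and PY = 1400 (rate 2.00 per 100).**
- Section 9.3.1: 100 × 1.96 × √0.02/1400 = 0.0198, so 1.98 to 2.02.
- Footnote b: 100 × 1.96 × √(0.02/1400) = 0.741, so 1.26 to 2.74. The exact Poisson interval is 1.33 to 2.89.
- Ratio of half-widths: 0.741/0.0198 = 37.4 = √1400.

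**Step 4: the assumed range, at 2 per 100 person-years.** Coverage of the nominal 95% interval is from 200,000 Poisson draws per row.

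| n, PY | Section 9.3.1 | Footnote b | √PY | Coverage, 9.3.1 | Coverage, footnote b |
|---|---|---|---|---|---|
| 4, 200 | 1.86 to 2.14 | 0.04 to 3.96 | 14.1 | 19% | 91% |
| 14, 700 | 1.96 to 2.04 | 0.95 to 3.05 | 26.5 | 11% | 93% |
| 20, 1000 | 1.97 to 2.03 | 1.12 to 2.88 | 31.6 | 9% | 95% |
| 28, 1400 | 1.98 to 2.02 | 1.26 to 2.74 | 37.4 | 8% | 94% |

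Other rates behave in the same way. At PY = 1400, n = 14 gives 0.99 to 1.01 against 0.48 to 1.52, and n = 56 gives 3.97 to 4.03 against 2.95 to 5.05.

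**Step 5: two checks that need no comparison with the shells.**
- Units: the rate is per year, but the section 9.3.1 margin is per year^1.5, so the interval depends on the time unit. For n = 28 and PY = 1400, working in person-months and converting back gives 1.994 to 2.006. Footnote b gives 1.26 to 2.74 either way.
- Event scale: multiplied by PY, the section 9.3.1 margin is 1.96 × √(n/PY) events. At 2 per 100 that is 1.96 × √0.02 = 0.28 of one event, however large the trial. At PY = 1400 the interval covers the true rate only when exactly 28 events occur, which explains the 8% coverage.

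**The case against.** The strongest reply is that the whole point rests on how far one root sign reaches, and that is easily lost when a displayed equation is converted from PDF to text. Both versions use the same elements in the same order. If the root on the page covers (n/PY)/PY, section 9.3.1 and the shells agree and there is no error. This stands as a condition on the finding, and it can be settled by looking at the page.

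It can also be said that the correct method is named in words in both documents and printed correctly in the footnotes for all four analyses, so a programmer following the shells gets the right interval. That holds for the rates in Tables 14.3.7.5 to 14.3.7.8. It does not reach the visit-schedule rates, or the optional centre and simulated-placebo rates.

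A reader might infer that section 9.3.1 overrides the shells, because SAP section 1 calls the appendices supporting material. The documents do not support that: the sentence only exempts formatting changes from signature approval, and neither version is named as governing. A reader might also infer that a falsely tight interval would make the comparison with IPM 027 placebo decisive. The SAP sets no test, margin or decision rule for that comparison, makes the Poisson interval for the simulated arm optional, and also gives that arm a percentile interval from 10,000 resamples. The protocol (section 8.4) treats incidence as a descriptive summary.

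**Conclusion.** The concern holds as a correction to the formula. As printed, the section 9.3.1 standard error is too small by exactly √PY, does not belong to the named method, and contradicts the correct footnote b. The √PY factor needs no assumed event count. Its value of about 14 to 37 rests on the assumed 200 to 1400 person-years, and the coverage figures also rest on an assumed rate of 2 per 100 person-years.

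The finding depends on the root being printed as read here. Even then, it does not show that any reported interval is wrong. The harm arises only where the section 9.3.1 formula was programmed, and the exposed rates are those without a shell. For a descriptive secondary endpoint this is a misstatement of precision, not a threat to a decision rule.

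**What to change.** 1. Check the extent of the root in section 9.3.1 on the PDF page. If it covers (n/PY)/PY, nothing further is needed on the formula.
2. If it is as printed here, replace the formula with [(n/PY) ± 1.96 × √n/PY] × 100.
3. State that this equals footnote b of Tables 14.3.7.5 to 14.3.7.8, and that it governs every seroconversion-rate interval using the Poisson normal approximation: overall, by centre, by visit schedule, and for any simulated-placebo rate.
4. Confirm which formula the code uses. The virology addendum SAP (section 6) cites an IPM 032 clinical study report dated 09 April 2020, so the check should include output already produced, especially tables built without a shell.

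The cost is one line of SAP text and one code check. No data collection or design feature changes.
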